### 4. Symptoms

Study participant will report their COVID-19 symptoms and scores at the screening call and will receive a paper copy and an emailed daily diary requesting information on COVID-19 symptoms, symptoms' severity scores and potential medication side effects. Participants who are unable to respond to emails will be asked to directly record this data into the provided paper study daily diary and then will be contacted daily to report this information to the study coordinator.

### 5. Vital Signs (to be collected for participants of sub-studies 1a and 1b only):

- Body temperature will be self-reported at Study Treatment Day 1, daily throughout the treatment period until two consecutive afebrile results are seen, and again at the End of Study Treatment Day 14.
- Study participants with a baseline diagnosis of hypertension will be instructed to take daily blood pressure measurements using a home blood pressure cuff. If they do not have access to a home blood pressure cuff, members of the study team will purchase one online and have it sent next-day. They are to contact the study team with any measurement of systolic blood pressure above 150 or below 90, as well as diastolic measurements above 90. Any measurements of SBP below 80 or above 180 will be advised to seek immediate medical attention as specified in section 15.
- Study participants with a baseline diagnosis of diabetes mellitus who are on insulin or sulfonylureas will be instructed to take blood sugar measurements in the morning, as well as three times daily before meals. If they do not have access to a home glucometer, members of the study team will purchase one online and have it sent next-day. Any measurements of blood glucose below 70 will be advised to eat a carbohydrate rich food and report to the study team, and measurements persistently below 70 will be advised to seek immediate medical attention as an immediate priority prior to reporting to the study team.
- Study participants with a baseline diagnosis of congestive heart failure or diuretic use will be required to monitor their weight daily and notify the study team if their weight changes by greater than 3 lbs (or 1.5 kg) throughout the 14 day trial period. If they do not have access to a home scale, members of the study team will purchase one online and have it sent via next-day delivery.
- Study participants who are not hospitalized yet remain febrile and report ongoing symptoms at EOT visit (Day 14) will continue to take their temperature and be contacted every 2-3 days by members of the study team until they are no longer symptomatic and are afebrile.

### 6. Adverse Events

- Adverse events are being monitored in three formats: daily communication with study team to report symptoms and adverse event reporting as described elsewhere (see section 15), labs at the end of the 14-day treatment period, and urgent reporting of adverse events via a 24 hour physician staffed phone line (see below). The study team will have a daily communication with subjects where our study coordinators will review all subjects' symptoms and their severity. This information will be tallied daily and will be reported to each site's PI and study main PI and medical monitor. Furthermore, they will be reported to the study DSMB and IRB.
- Information regarding occurrence of adverse events will be captured on the IRB approved standard case report form (CRF) as follows: Duration (start and stop dates and times), severity/grade, outcome, and relation to study medication).

- Any deterioration in cardiac or pulmonary status will be immediately escalated to proper medical attention and that any study participant who is hospitalized for any reason will be required to stop study medication irrespective of the cause of this adverse event. These events will subsequently be reported to the DSMB and IRB for review.
- A list of anticipated side effects of FoTv or mQFPD will be available to study coordinators, as will a list of known symptoms of COVID-19. Any reported symptom on the COVID-19 list will be referred to the study participant's primary care provider.

### **Clinical Laboratory Measurements:**

Sub-studies 1a and 1b:

Sample collection (nasal swab and approximately 25 mL of whole blood with an additional 50 mL whole blood optional) will occur at two time points: (1) screening/baseline and (2) end-of-study. The purpose of the time point (1) sample collection will be to obtain specimens for both screening and baseline clinical laboratory tests. The additional 50 mL of whole blood will allow for in-depth analysis of the peripheral mononuclear cell, including rare immune cell subsets. This collection is optional. The purpose of the time point (2) sample collection will be to obtain specimens for end-of-study clinical laboratory tests.

#### **(1) Screening/Baseline:**

##### **Screening:**

The following laboratory tests will be conducted and reviewed prior to study initiation to confirm that liver and renal failure (exclusion criteria) are not present:

- Basic Metabolic Panel
- Liver Function Testing
- Prothrombin Time and Partial Thromboplastin Time

##### **Baseline:**

The following laboratory assays will be conducted to establish baseline values for safety measures:

- Complete Blood Count with Differential
- Ferritin
- D-Dimer
- Lactate Dehydrogenase
- C-Reactive Protein
- Troponin
- T-cell differentiation panel
- Additionally, plasma, serum, and whole blood will be collected and banked for cytokine, immunological, and metabolomic assays.

Please note that nasal swab or salivary samples will be collected at day 0 (baseline) as well as at days 7 and 14 for all subjects.

A urine home pregnancy test will be delivered to women of childbearing potential and the results will be self-reported to the study team prior to starting study medication.

#### **(2) End-of-Treatment:**

For patients who are not hospitalized, the study phlebotomist will collect their specimens at Day 14 for the following laboratory tests:

- Basic Metabolic Panel
- Complete Blood Count with Differential
- Liver Function Testing

- Prothrombin Time and Partial Thromboplastin Time
- Ferritin
- D-Dimer
- Lactate Dehydrogenase
- C-Reactive Protein
- Troponin
- T-cell differentiation panel
- Salivary or nasal swab samples will be collected for SARS CoV-2 viral load assays
- Plasma, serum, and whole blood will be collected and banked for cytokine, immunological, and metabolomic assays

For subjects who require hospitalization by Day 14, results of the following laboratory tests will be obtained from their hospital records (please note that these tests are routinely conducted as part of COVID-19 treatment and results should be available within subjects' medical records):

- Admission Basic Metabolic Panel,
- Complete Blood Count with Differential, and
- Liver Function Testing.

Please note that medical records will also be reviewed for SARS-CoV-2 viral load, any inflammatory biomarkers (CRP, procalcitonin, IL-6, ferritin, D-dimer, lactate dehydrogenase) as well as markers of myocarditis (troponin, CK-MB) and further lymphocyte differentiation (T-Cell differentiation panel).

Sub-study 1c:

Sample collection will occur at the following time points:

- Single dose vaccine (such as J&J): baseline, day 14, day 28, and 6 months post vaccination
- Two-dose vaccine (such as Pfizer or Moderna): baseline, day 14, two weeks after your second dose, and 6 months post vaccination
- Vaccine booster: baseline, day 3, day 14, and 6 months

For all time points:

The following test will be run to establish values of immunogenicity against SARS CoV-2:

- SARS CoV-2 IgG antibody titer
- Cytokines and T-cell assays

For time points Baseline and Day 14:

The following laboratory assays will be conducted to ascertain FoTv safety:

- Basic Metabolic Panel
- Liver Function Tests

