#### A. Safety:

The following safety data will be collected and assessed during the study:

- 1) Incidence and severity of adverse events
- 2) Laboratory evaluations
- 3) Home glucometer measurements for diabetic participants
- 4) Home blood pressure measurements for hypertensive participants
- 5) Home daily weight measurements for patients with congestive heart failure or diuretic use

Safety data will be collected and assessed using the following methods:

- 1) Each participant will receive a paper copy and an emailed daily diary requesting information on symptoms (including duration and severity), vitals, and medication compliance. Participants who are unable to respond to emails will be asked to directly record this data into the provided paper study daily diary and then will be contacted daily to report this information to the study coordinator. All email exchanges among study personnel will be conducted within the UC intranet secure system. All communications with patients will be through virtual appointments using UC secure systems, UC San Diego encrypted emails or with password-protected study documents.
- 2) Study coordinators will collect and enter all safety data. All serious adverse events (SAEs) will, per UCSD IRB guidelines, be reported to the IRB and DSMB within 3 business days of learning of the event. Any adverse events, as well as any escalation of care, including urgent care, emergency room, or hospitalization, will be reported to the study team after appropriate medical care has been received, via a dedicated phone number or email address that is specific for urgent matters.
- 3) The UCSD site will implement a Data and Safety Monitoring Board (DSMB) to review data safety and monitoring as part of their responsibilities. The DSMB will include two senior researchers and a consumer representative. They will have conference calls bi-weekly (or more frequently, if needed).
- 4) The study biostatistician will send a tabulated symptom and adverse event report daily to all sites and to the study PI and weekly to the study DSMB and IRB.
- 5) The safety of the study medication will also be assessed through laboratory data collection at baseline, and at either the end of the treatments following end of quarantine (for non-hospitalized patients) or as part of hospital admission labs (for patients requiring hospitalization)
  - a. Basic Metabolic Panel
  - b. Complete Blood Count with Differential
  - c. Liver Function Testing

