  - d. Prothrombin Time and Partial Thromboplastin Time

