## **9. RESEARCH DESIGN AND METHODS**

The following research design applies to each of the following studies:

Sub-study 1a: FoTv vs. placebo for acute COVID-19 patients

Sub-study 1b: QFPD vs. placebo for acute COVID-19 patients

Sub-study 1c: FoTv vs. placebo as an adjunct to COVID-19 vaccination

Sub-studies 1a and 1b of Phase 1 trial will each be 2-arm multicenter double blind randomized placebo controlled clinical trials.

Each of these safety/feasibility sub-studies will be conducted identically with the exception of additional exclusion criteria that will be required for sub-study 1b on account of the presence of herbal components including ephedrine that require these precautions for avoiding herb-drug interactions.

Sub-study 1c will be a single site double blind randomized placebo controlled clinical trial.

This will be a shorter intervention with broader inclusion criteria.

The research design and methods for the larger efficacy trial (Phase 2) will require analysis of these first two feasibility studies, and the final protocol will be submitted as a future amendment.

The primary objective of sub-studies 1a and 1b will be to assess the safety of FoTv or mQFPD, respectively, when used as therapies for acute COVID-19 infection and feasibility of the study protocol.

The primary objectives of sub-study 1c will be to ascertain the safety of FoTv when used as an adjunct to standard COVID vaccination as well as to evaluate its effects on post-vaccine COVID-19 antibody titers and on vaccination-related side effects.

A total of 66 subjects (33 FoTv or mQFPD and 33 placebo) will be enrolled in each of the 1a and 1b sub-studies.

A total of 266 subjects (133 FoTv and 133 placebo) will be enrolled in sub-study 1c.

The study protocol will be implemented and safety, feasibility, clinical, and laboratory data will be collected.

Interested participants will be asked to contact the study team, who will then conduct screening, consenting, and study enrollment. The study will be open to patients who are

- a) Mildly-to-moderately symptomatic and have tested positive for COVID-19 (sub-studies 1a and 1b)
- b) Scheduled for COVID-19 vaccination (sub-study 1c).

See section 11 for recruitment plan.

Once their eligibility has been confirmed, participants will be randomized to one of two groups by the study statistician:

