#### **HIPAA Authorization waiver is requested for three reasons:**

- To facilitate recruitment (as described above)
- The PHI will be used for three discrete purposes: To identify COVID-19 patients with confirmatory test and have a means for direct communication within this narrow time window. Note that for those individuals who decline to participate, any identifying information will be destroyed.
- To collect end-of-study data from any patients that are hospitalized during their involvement in the study, in order to 1) compare admission laboratory evaluations to baseline laboratory evaluations to determine safety, and 2) provide sufficient data for an endpoint adjudication committee to determine if primary and secondary endpoints were met. This component is minimal risk because the data analysis will be done retrospectively and will not impact the medical care of the study participant.

The data gathered as described above will explicitly be used only for the purposes of this study and will not be used for marketing, recruitment, or shared with anybody outside of the authorized members of the study team. Once collected, PHI will be removed and replaced with a unique patient identifier for analysis. The PHI will only be reviewed by properly trained and authorized study team members. Only eligibility criteria will be accessed/reviewed.

The measures described elsewhere in this document to protect the privacy of study participants will also be applied to these data. As with any digital technology, even the most secure data networks are at times subject to compromise. However, this small risk is outweighed by the direct benefit to the study participant of having accurate prior laboratory data to confirm their safety.

We plan to:

- Protect identifiers from improper use and disclosure. The data will not be used as a part of the research data. Only properly trained and delegated study team members will be authorized to perform the screening/chart review.
- Destroy identifiers at the earliest opportunity or provide justification for retaining the identifiers. All identifiers will be destroyed immediately after reviewing the daily list with the doctor. No PHI will be stored or utilized, unless a potential subject has agreed to participate, consented and signed a HIPAA authorization to do so.

The PHI data will not be re-used or disclosed for other purposes

Subjects will be granted a copy of the final study publication on request.

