#### Virulogic risk

According to the WHO, approximately 81% cases of COVID-19 are mild to moderate, and severe disease may require hospitalization in approximately 19% of cases. A total of approximately 5-10% of COVID-19 patients may ultimately require ICU level of care which may include intubation. The CDC estimates the case fatality rate among COVID-19 patients is expected to be between 0.25-3%, with a dramatic increase in death rate among older populations (10 to 27% among persons aged >84 years old). These statistics may change as we learn more about the disease.

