#### Loss of confidentiality

### **15. RISK MANAGEMENT PROCEDURES AND ADEQUACY OF RESOURCES**

Subjects will be monitored throughout the study and their symptoms will be recorded and reviewed by the medical monitor on a daily basis during the active phase of treatment.

Safety of the study medication will also be assessed through laboratory data collection either at the end of the treatments (for non-hospitalized patients) or on hospital admission (utilizing labs on admission for hospitalized patients)

Study participants will be advised to report any skin eruptions to the study team and to stop medication immediately until they can be interviewed by our medical monitor who will make the assessment of allergy.

Respiratory allergies such as asthma exacerbations will be treated as COVID-19 exacerbations, where medication will be stopped and participants will be directed to immediate medical attention. An adverse event will be logged, and relation to the study medication will be determined per protocol.

In an event of participants requiring immediate medical attention, the study team will first refer the patient to contact their primary care physician if they are in close communication. If they are not, the study team will provide the participant with a short list of telephone numbers that patients can call to seek immediate medical attention. This will be specific to Southern California and will include 24-hour hotlines that are run by insurance companies, healthcare centers, and regional governments. If none are appropriate, they will be directed to dial 911.

All serious adverse events (SAEs) will, per UCSD IRB guidelines, be reported to the IRB and DSMB within 3 business days of learning of the event. The study biostatistician will send a tabulated symptom and adverse event report daily to all sites and to the study PI and weekly to the study DSMB and IRB.

Any adverse events, as well as any escalation of care, including urgent care, emergency room, or hospitalization, will be reported to the study team after appropriate medical care has been received, via a dedicated phone number or email address that is specific for urgent matters.

The UCSD site will implement a Data and Safety Monitoring Board (DSMB) to review data safety and monitoring as part of their responsibilities. The DSMB will include two senior researchers, and a consumer representative. They will have a conference call bi-weekly (or more frequently, if needed).

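### In sub-studies 1a and 1b, hospital-admission labs stand in for end-of-treatment labs with no rule for keeping the two apart, and the hospital retrieval list omits PT/PTT

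*Combined protocol and SAP*

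**What the plan says.** Section 9 makes safety a primary objective: "The primary objective of sub-studies 1a and 1b will be to assess the safety of FoTv or mQFPD". Section 6 (A. Safety, for 1a and again for 1b) lists laboratory evaluations among five kinds of safety data. It sets a baseline draw and then one further set of labs, taken either at the end of treatment "or as part of hospital admission labs (for patients requiring hospitalization". Section 15 repeats the rule: the later labs are taken at the end of treatment or "on hospital admission (utilizing labs on admission for hospitalized patients".

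Section 9, (2) End-of-Treatment, puts both sources under one heading. For one group, "For patients who are not hospitalized, the study phlebotomist will collect their specimens at Day 14". For the other, "For subjects who require hospitalization by Day 14, results of the following laboratory tests will be obtained from their hospital records". The hospital list that follows has three items: metabolic panel, blood count and liver tests. A further record review covers viral load, inflammatory markers, markers of myocarditis and lymphocyte differentiation. Neither list names PT/PTT. Section 6 does name it, as the fourth of the four safety labs under the either/or rule: "Prothrombin Time and Partial Thromboplastin Time".

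The Section 9 description of sub-studies 1a and 1b sends only participants who have not been hospitalized to the Day-14 draw. Statistical Methods And Considerations plans ANOVA or chi-square tests of safety data at each time point, rank tests and a confirmatory mixed model, in all randomized subjects. It does not mention admission labs. The HIPAA waiver text in Section 12 gives one use for them: to "compare admission laboratory evaluations to baseline laboratory evaluations to determine safety".

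**The concern.** For anyone admitted by Day 14, the admission value is the only post-baseline safety lab that the plan specifies, and it is filed under End-of-Treatment. An analyst with two scheduled lab time points and no further instruction could reasonably enter it at the second one. The end-of-treatment mean in each arm would then average Day-14 values with values from an earlier day, taken in a different clinical state and, because study medication stops at hospitalization, after a shorter exposure.

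If the arms differ in hospitalization, the lab comparison can move because the mix differs, with no direct effect of the product on the lab value. The plan foresees such a difference in both directions. Section 14 reports the FDA's question whether FoTv could worsen COVID-19, and Section 17 names a lower risk of hospitalization as a possible benefit. If the rates are equal there is no such shift, but the spread grows.

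The PT/PTT gap matters for a related reason. If the test is not retrieved, its missingness follows the clinical outcome, and only hospitalized participants lose it.

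**Working it through.** **Denominator.** Sample Size Justification gives 27 per arm plus 6 for 20% dropout: 27 + 6 = 33, and 33 × 2 = 66. This reproduces the plan's figure, which is not in dispute. The calculations below use 27 evaluable per arm unless stated.

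**Share hospitalized, p.** Section 14 (Virulogic risk) says "severe disease may require hospitalization in approximately 19% of cases". This is a background figure for COVID-19 cases in general, not a trial assumption. The trial excludes people whose symptoms already call for hospitalization, so 19% is treated as an upper value and 5% and 10% are shown beside it. Expected admissions per arm are:

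| p | of 27 | of 33 |
|---|---|---|
| 5% | 1.4 | 1.7 |
| 10% | 2.7 | 3.3 |
| 19% | 5.1 | 6.3 |

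At 5%, the chance of at least one admission-based value among 54 participants is 1 − 0.95^54 = 94%. The handling question will almost certainly arise.

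**Distance, s.** This is how far admission values lie from Day-14 values, in SD units. The documents give no figure. The main range assumed is 1 to 2, with 3 as an extreme.

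**Equal rates.** SD of the mixed value = sqrt(1 + p(1 − p)s²).
- p = 19%: sqrt(1 + 0.1539) = 1.07 for s = 1; sqrt(1 + 0.6156) = 1.27 for s = 2.
- p = 5%: sqrt(1 + 0.0475) = 1.02 for s = 1; sqrt(1 + 0.19) = 1.09 for s = 2.

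Power for an illustrative 0.8 SD lab difference is 83.6% with no mixing. It falls to 78% (s = 1) or 64% (s = 2) at p = 19%, and to 82% or 77% at p = 5%. In simulation at p = 19% the rejection rate under no effect stays at about 5%.

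**Unequal rates, no effect of product on the lab.** Spurious difference = (difference in p) × s. The last column comes from 20,000 simulated two-sample t-tests per setting at a nominal 5%. All pairs of rates are assumptions.

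| Rates | s | Shift (SD) | Rejection rate |
|---|---|---|---|
| 5% vs 10% | 1 | 0.05 | 5.2% |
| 5% vs 10% | 2 | 0.10 | 6.0% |
| 10% vs 19% | 1 | 0.09 | 5.9% |
| 10% vs 19% | 2 | 0.18 | 8.2% |
| 10% vs 19% | 3 | 0.27 | 10.2% |
| 5% vs 19% | 1 | 0.14 | 7.8% |
| 5% vs 19% | 2 | 0.28 | 13.7% |

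For scale, the standard error of an arm difference is sqrt(2/27) = 0.27 SD.

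**PT/PTT.** This part needs no assumption. Section 6 puts four labs under the either/or rule, the Day-14 list for non-hospitalized participants includes all four, and the hospital list includes three. PT/PTT is the one left out.

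**The case against.** The strongest reply is that the plan never says admission values enter a Day-14 test. The one use it states, in Section 12, is a within-person comparison with baseline. That is right: a reader might infer that pooling is planned, but the documents support only that handling is unspecified and that pooling is a natural reading.

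A reader might also picture admission labs drawn at the worst moment and Day-14 labs drawn after recovery. The documents state neither. The Vital Signs text in Section 9 expects some non-hospitalized participants to be febrile and symptomatic at Day 14.

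The reply also notes that labs are one safety measure among five, that adverse events are tabulated by arm anyway, and that rank tests and transformations are planned. All true. The SD and mean-shift figures describe the ANOVA. A rank test depends less on how far out the admission values lie, but an unequal mix still affects it.

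On PT/PTT, Section 9 has the team obtain laboratory records from the hospitalization, which permits retrieval. So the test is at risk of being missing; it is not established that it will be.

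Finally, simply dropping admission labs would be a poor remedy. It conditions a safety comparison on a post-randomization event and sits badly with analysing all randomized subjects. The planned mixed model assumes data missing at random, and with only baseline and Day 14 it cannot repair losses driven by deterioration. This objection stands in full and shapes the fix.

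**Conclusion.** The point holds as a gap in specification plus a mismatch between lists, confined to the laboratory part of safety in 1a and 1b. Adverse-event counts and sub-study 1c are not affected.

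The plan lets two lab sources share the end-of-treatment slot and gives no rule to separate them. If they are pooled and hospitalization differs by arm, the comparison shifts. At 10% versus 19% with a 1 to 2 SD distance the shift is 0.09 to 0.18 SD, which is less than one standard error; at 5% versus 10% it is 0.05 to 0.10 SD. The distance and the arm-specific rates are assumptions, and 19% is a background figure taken as an upper value. These figures do not show that the safety comparison is invalid or that its error rate is generally inflated: with equal rates it stays near 5%. They show that an avoidable ambiguity can move a result by a modest amount.

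The PT/PTT omission is a plain inconsistency between Section 6 and the hospital list in Section 9.

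**What to change.** 1. Add PT/PTT to the hospital-record list in Section 9, (2) End-of-Treatment, to match Section 6 for both sub-studies. The plan's remark that the listed tests are routine in hospital was made for a list without PT/PTT, so record separately whether it was not done or not retrieved.
2. Record the study day of each hospital lab and label it as admission. Tabulate admission values and change from baseline by arm, beside the number hospitalized in each arm.
3. State in Statistical Methods And Considerations that the end-of-treatment lab comparison will be reported both with and without admission values. Note there that the version without them conditions on a post-randomization event, so neither version is read alone.

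The cost is a little more data abstraction and one more set of tables. The sample size and visit schedule do not change.
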